#### **4.4.3 Secondary Efficacy Analysis**

Results will be reported for observed data only; missing values will not be imputed.

##### **4.4.3.1 ODI Responder Rates**

Responder rates for ODI will be determined by the proportion of subjects who achieve  $\geq 10$ ,  $15$ , and  $20$ -point reductions in ODI from Baseline to 5+ years post-treatment.

##### **4.4.3.2 Pain Score**

The mean change will be analyzed with an ANCOVA with a covariate of baseline VAS score. See Appendix A - Table 9.

Responder rates for numeric pain scores (VAS scale 0 to 10) will be determined by the proportion of subjects who achieve  $\geq 1.5$  and  $2.0$  point reductions in pain score from Baseline to 3 months.

##### **4.4.3.3 Regression to the Mean**

Regression to the mean analyses for ODI and VAS will be performed as supplemental analyses. See Appendix A - Table 11.

 relevant medsystems	CD_3012_Rev B  Five-Plus Year Follow-Up of SMART Trial Statistical Analysis Plan	Date Effective: November 5, 2019  Page 11 of 21
---	---	--

#### 4.4.3.4 Treatment Success

Intracept long term treatment success rates will be determined by the proportion of subjects who meet the composite definition of treatment success at 5+ years.

#### 4.4.3.5 Patient Satisfaction

The Patient Satisfaction survey responses will be summarized using descriptive statistics.

	CD_3012_Rev B Five-Plus Year Follow-Up of SMART Trial Statistical Analysis Plan	Date Effective: November 5, 2019 Page 12 of 21
---	--	---

## 5. APPENDIX A – ANALYSIS TABLES

Table 1 - Summary of Screening (Enrolled Subjects)	
	SMART 5+ Year US Treatment Arm Cohort (N=132)
Enrolled (Consented)	% (n/N)
Study Non-Participation Reason	% (n/N)
Declined Participation	% (n/N)
Subject Withdraw Consent	% (n/N)
LTFU	% (n/N)
Death	% (n/N)
Other	% (n/N)

Table 2 - Demographic Information			
Characteristic	SMART Treated Subjects in 5+ Yr Follow-up N = XX	SMART Treated Subjects Not in 5+ Year Follow-up N = XX	t-test of Means or Exact Test of Proportions
Age (years)	Mean + SD, Median, Range	Mean + SD, Median, Range	
Gender:			
Male	% (n/N)	% (n/N)	
Female	% (n/N)	% (n/N)	

Table 3 – Baseline Social/Socioeconomic/Work History			
Characteristic	SMART Treated Subjects in 5+ Yr Follow-up N = XX	SMART Treated Subjects Not in 5+ Year Follow-up N = XX	t-test of Means or Exact Test of Proportions
Baseline Working Status			
Working	% (n/N)	% (n/N)	
Working Full-Time	% (n/N)	% (n/N)	
Working Part-Time	% (n/N)	% (n/N)	
Not Working	% (n/N)	% (n/N)	
Short-Term Disability	% (n/N)	% (n/N)	
Not Working Due to Back Pain	% (n/N)	% (n/N)	
Unemployed	% (n/N)	% (n/N)	
Retired	% (n/N)	% (n/N)	
Other	% (n/N)	% (n/N)	
Time since last worked (for subject not working due to back pain)	Mean + SD, Median, Range	Mean + SD, Median, Range	

	CD_3012_Rev B Five-Plus Year Follow-Up of SMART Trial Statistical Analysis Plan	Date Effective: November 5, 2019 Page 13 of 21
---	---	--

Table 4 – Baseline Characteristics			
Characteristic	SMART Treated Subjects in 5+ Yr Follow-up N = XX	SMART Treated Subjects Not in 5+ Year Follow-up N = XX	t-test of Means
Baseline ODI	Mean + SD, Median, Range	Mean + SD, Median, Range	
Baseline VAS	Mean + SD, Median, Range	Mean + SD, Median, Range	

Table 5 – Baseline Low Back Pain History			
Characteristic	SMART Treated Subjects in 5+ Yr Follow-up N = XX	SMART Treated Subjects Not in 5+ Year Follow-up N = XX	t-test of Means or Exact Test of Proportions
Length of Time Experience LBP			
< 6 months	% (n/N)	% (n/N)	
6 months to < 1 year	% (n/N)	% (n/N)	
1 year to < 2 years	% (n/N)	% (n/N)	
2 years to < 3 years	% (n/N)	% (n/N)	
3 years to < 5 years	% (n/N)	% (n/N)	
> 5 years	% (n/N)	% (n/N)	
# of days a Week Subject Experiences Low Back Pain	Mean + SD, Median, Range	Mean + SD, Median, Range	
Modic Type by Level & Endplate			
L3 Superior Endplate	% (n/N)	% (n/N)	
Modic I	% (n/N)	% (n/N)	
Modic II	% (n/N)	% (n/N)	
L3 Inferior Endplate	% (n/N)	% (n/N)	
Modic I	% (n/N)	% (n/N)	
Modic II	% (n/N)	% (n/N)	
L4 Superior Endplate	% (n/N)	% (n/N)	
Modic I	% (n/N)	% (n/N)	
Modic II	% (n/N)	% (n/N)	
L4 Inferior Endplate	% (n/N)	% (n/N)	
Modic I	% (n/N)	% (n/N)	
Modic II	% (n/N)	% (n/N)	
L5 Superior Endplate	% (n/N)	% (n/N)	
Modic I	% (n/N)	% (n/N)	
Modic II	% (n/N)	% (n/N)	
L5 Inferior Endplate	% (n/N)	% (n/N)	
Modic I	% (n/N)	% (n/N)	
Modic II	% (n/N)	% (n/N)	
S1 Superior Endplate	% (n/N)	% (n/N)	
Modic I	% (n/N)	% (n/N)	
Modic II	% (n/N)	% (n/N)	

relevant medsystems	CD_3012_Rev B  Five-Plus Year Follow-Up of SMART Trial Statistical Analysis Plan	Date Effective: November 5, 2019  Page 14 of 21
-------------------------------	---	--

Table 6 – Baseline Low Back Treatment History			
Characteristic	SMART Treated Subjects in 5+ Yr Follow-up N = XX	SMART Treated Subjects Not in 5+ Year Follow-up N = XX	t-test of Means or Exact Test of Proportions
Medications			
Opioid Medications	% (n/N)	% (n/N)	
Total Opioid Equianalgesic Average Daily Dose in 7 days prior to Baseline	Mean + SD, Median, Range	Mean + SD, Median, Range	
Injections	% (n/N)	% (n/N)	
Epidural Injections	% (n/N)	% (n/N)	
Facet Injections	% (n/N)	% (n/N)	
Other Injections	% (n/N)	% (n/N)	

Table 7 – RF Ablation Table			
Characteristic	SMART Treated Subjects in 5+ Yr Follow-up N = XX	SMART Treated Subjects Not in 5+ Year Follow-up N = XX	t-test of Means or Exact Test of Proportions
VB Treated			
L3	% (n/N)	% (n/N)	
L4	% (n/N)	% (n/N)	
L5	% (n/N)	% (n/N)	
SI	% (n/N)	% (n/N)	

	CD_3012_Rev B Five-Plus Year Follow-Up of SMART Trial Statistical Analysis Plan	Date Effective: November 5, 2019 Page 15 of 21
---	--	---

**5+ Year Follow-up Study Endpoints:**

Tables 8 and 9 will be performed for both the ITT (as treated) population and the Intracept treated only population.

Table 8 – Primary Endpoint Results	
	SMART 5+ Yr Follow-up Subjects N = XX Mean ± SD (N), Median [Interquartile Range], Range or % (n/N)
Time of Assessment	
Years since Index Procedure	Mean + SD, Median, Range
Percent with at Least 5 years of Follow-up	% (n/N)
ODI	(N=XX)
Baseline ODI Score (Mean + SD, Median, Range)	Mean + SD, Median, Range
5+ Year ODI Score (Mean + SD, Median, Range)	Mean + SD, Median, Range
Mean change in ODI score from baseline to 5+ Years post-treatment	Mean + SD, Median, Range ( p-value )
ODI Responder Rates	
Subjects with ≥ 10-point ODI decrease	% (n/N) ( p-value )
Subjects with ≥ 15-point ODI decrease	% (n/N) ( p-value )
Subjects with ≥ 20-point ODI decrease	% (n/N) ( p-value )
ODI Response Quartiles	
Subjects with ≤ 24% or less decrease	% (n/N)
Subjects with 25-49% decrease	% (n/N)
Subjects with 50-74% decrease	% (n/N)
Subjects with 75-100% decrease	% (n/N)
	(p-value)

	CD_3012_Rev B Five-Plus Year Follow-Up of SMART Trial Statistical Analysis Plan	Date Effective: November 5, 2019 Page 16 of 21
---	--	---

Table 9 – Secondary Endpoints Results	
	SMART 5+ Yr Follow-up Subjects N = XX
10 Point VAS Numeric Pain Scale	
Baseline VAS Score (Mean + SD, Median, Range)	Mean + SD, Median, Range
5+ Year VAS Score (Mean + SD, Median, Range)	Mean + SD, Median, Range
Mean change in VAS score from baseline to 3 months post-treatment	Mean + SD, Median, Range ( p-value )
VAS Responder Rates	
% of subjects with $\geq$ 1.5 Pt VAS decrease	% (n/N) ( p-value )
% of subjects with $\geq$ 2.0 Pt VAS decrease	% (n/N) ( p-value )
VAS Response Quartiles	
Subjects with $\leq$ 24% or less decrease	% (n/N)
Subjects with 25-49% decrease	% (n/N)
Subjects with 50-74% decrease	% (n/N)
Subjects with 75-100% decrease	% (n/N)
	( p-value )

Table 10 – Regression to the Mean Analysis	
	SMART 5+ Yr Follow-up Subjects N = XX
Regression to the Mean	
Average change in ODI in CONTROL group between baseline and 1 year	Mean, N, 95% CI, t-test p (Ho: $\delta=0$ )
Average change in ODI in CONTROL group between baseline and 2 years	Mean, N, 95% CI, t-test p (Ho: $\delta=0$ )
Average change in ODI in INTRACEPT group between baseline and 1 year	Mean, N, 95% CI, t-test p (Ho: $\delta=0$ )
Average change in ODI in INTRACEPT group between baseline and 2 years	Mean, N, 95% CI, t-test p (Ho: $\delta=0$ )
Average change in ODI in INTRACEPT group between baseline and 5+ years	Mean, N, 95% CI, rm F-test p (Ho: $\delta=0$ )
Time (per year) effect on ODI in INTRACEPT group	Mean, N, 95% CI, rm F-test p (Ho: time=0)
Average change in VAS in CONTROL group between baseline and 1 year	Mean, N, 95% CI, t-test p (Ho: $\delta=0$ )
Average change in VAS in CONTROL group between baseline and 2 years	Mean, N, 95% CI, t-test p (Ho: $\delta=0$ )
Average change in VAS in INTRACEPT group between baseline and 1 year	Mean, N, 95% CI, t-test p (Ho: $\delta=0$ )
Average change in VAS in INTRACEPT group between baseline and 2 years	Mean, N, 95% CI, t-test p (Ho: $\delta=0$ )
Average change in VAS in INTRACEPT group between baseline and 5+ years	Mean, N, 95% CI, t-test p (Ho: $\delta=0$ )
Time (per year) effect on VAS in INTRACEPT group	Mean, N, 95% CI, rm F-test p (Ho: time=0)

	CD_3012_Rev B Five-Plus Year Follow-Up of SMART Trial Statistical Analysis Plan	Date Effective: November 5, 2019 Page 17 of 21
---	--	---

Table 11 – Comparison of SMART Endpoints			
Characteristic	SMART Treated Subjects in 5+ Yr Follow-up N = XX	SMART Treated Subjects Not in 5+ Year Follow-up N = XX	t-test of Means or Exact Test of Proportions
Change in ODI (Baseline to 3 Months)	Mean + SD, Median, Range	Mean + SD, Median, Range	
Change in VAS (Baseline to 3 Months)	Mean + SD, Median, Range	Mean + SD, Median, Range	
ODI Responders ( $\geq$ point ODI reduction)	% (n/N)	% (n/N)	

Table 12 – Opioids & Injections Utilization	
SMART 5+ Yr Follow-up Subjects N = XX	
Opioid Use	
Subjects Taking Opioids at Baseline	% (n/N)
Subjects actively taking Opioids in last 30 days (5+ Year Follow-up Visit)	% (n/N)
Opioid Dosage (in subjects taking opioids)	
Opioid Dosage at Baseline	Mean + SD, Median, Range
Opioid Dosage at 5+ years post treatment	Mean + SD, Median, Range
Epidural Injections	
Subjects with prior injections at baseline	Mean + SD, Median, Range
Subjects with injections in 12 months prior to 5+ year post treatment visit	Mean + SD, Median, Range
Subjects with injections for low back pain treatment in the same location as Intracept treatment (in the past 12 months):	Mean + SD, Median, Range
Mean # of injections per subject in 12 months prior to baseline	% (n/N)
Mean # of injections per subject in 12 months prior to 5+ year post treatment visit	% (n/N)
Time to first injection for low back pain in same location post Intracept Procedure	Mean + SD, Median, Range

	CD_3012_Rev B Five-Plus Year Follow-Up of SMART Trial Statistical Analysis Plan	Date Effective: November 5, 2019 Page 18 of 21
---	--	---

Table 13 – Surgical Interventions	
	SMART 5+ Yr Follow-up Subjects N = XX
Number (%) of subject reporting a procedure	% (n/N)
Number of procedures	% (n/N)
Re-intervention Rate over Time	
1 Year	S% (95% CI)
2 Year	S% (95% CI)
5 Year	S% (95% CI)
Type of procedure:	
Discectomy	% (n/N)
Lumbar fusion	% (n/N)
RF Ablation	% (n/N)
Other	% (n/N)
At the same level of Intracept treatment?	
Yes	% (n/N)
No	% (n/N)
Time to intervention (post Intracept procedure)	Mean + SD, Median, Range
Same etiology and level as Intracept treatment	Mean + SD, Median, Range
Different etiology or level from Intracept treatment	Mean + SD, Median, Range

Table 14 – Pain Status at 5 + Years	
	SMART 5+ Yr Follow-up Subjects N = XX
Pain Status	
Constant	% (n/N)
Intermittent	% (n/N)
No Pain	% (n/N)
Experiencing Pain	
Same location as prior to Intracept Procedure	% (n/N)
Different location from prior to Intracept Procedure	% (n/N)
Same nature as prior to Intracept Procedure	% (n/N)
Different nature from prior to Intracept Procedure	% (n/N)
Time (per year) effect on VAS in INTRACEPT group	Mean, N, 95% CI, rm F-test p (Ho: time=0)

	CD_3012_Rev B Five-Plus Year Follow-Up of SMART Trial Statistical Analysis Plan	Date Effective: November 5, 2019 Page 19 of 21
---	--	---

Table 15 – Durability at 5 + Years	
	SMART 5+ Yr Follow-up Subjects N = XX
Number (%) of subjects reporting a re-intervention (lumbar procedure adjudicated as same location and etiology as Intracept procedure)	% (n/N)
Number (%) of subjects reporting actively using opioids (defined as > 25% of total prescribed dosage in 30 days prior to visit)	%(n/N)
Number (%) of subjects reporting low back pain injections in same treatment location as Intracept.	% (n/N)
Number (%) of subjects reporting less than 2 point decrease in pain (in same location) compared to baseline	% (n/N)
Number (%) of subjects reporting less than 10 point decrease in ODI compared to baseline	% (n/N)
Number (%) of subjects reporting at least one of the above	% (n/N)
Intracept therapy success rate at 5 plus years (none of the below criteria are met)	% (n/N)

The following is the definition of therapy success:
 
 
a. ODI decrease of 10 or more at 5+ years
 
b. VAS decrease of 2 or more at 5 + years
 
c. No procedures since the Intracept procedure (that is adjudicated as treatment failure due to same location, same etiology, same severity as baseline)
 
d. No injections (in past 12 months and adjudicated as for same location, etiology, severity as baseline)
 
e. Not actively taking opioids (defined as > 25% of total dosage in 30 days prior to study visit)
 
	

	CD_3012_Rev B Five-Plus Year Follow-Up of SMART Trial Statistical Analysis Plan	Date Effective: November 5, 2019 Page 20 of 21
---	---	--

Table 16 – Patient Satisfaction	
	Subject Frequency
How do you feel your condition is post the Intracept Procedure?	
Improved	% (n/N)
Slightly	% (n/N)
Much	% (n/N)
Vastly	% (n/N)
No Change	% (n/N)
Worsened	% (n/N)
Slightly	% (n/N)
Much	% (n/N)
Vastly	% (n/N)
I am satisfied with the results of my surgery	
Yes	% (n/N)
No	% (n/N)
All things considered; I would have the surgery again for the same condition	
Yes	% (n/N)
No	% (n/N)
Were you able to resume the activity level you enjoyed prior to onset of your low back pain?	
Yes	% (n/N)
No	% (n/N)

	CD_3012_Rev B Five-Plus Year Follow-Up of SMART Trial Statistical Analysis Plan	Date Effective: November 5, 2019 Page 21 of 21
---	--	---

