## 2. STUDY DESIGN

### 2.1 Overall Study Design

This study is a post-market, non-interventional, data collection of the long term (5 + year) follow-up in the 133 treatment arm subjects in the SMART trial in the U.S. The study will be conducted at the same thirteen U.S. study sites where the procedures occurred.

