### 2.3 Study Population

All US subjects that were randomized to the treatment arm of the original SMART Trial will be approached to participate in the long term (5 + year) follow-up study. A single study visit will be performed by an independent nurse CRA to collect the data.

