#### 4. STATISTICAL AND ANALYTICAL PLANS

##### 4.1 General Methodology

The SMART Five Plus Year Follow-up Study analysis will be performed when all US SMART treatment arm subjects have been approached to participate in the study, and all subjects who consented to participate, have completed their 5+ year follow-up study visit.

	CD_3012_Rev B Five-Plus Year Follow-Up of SMART Trial Statistical Analysis Plan	Date Effective: November 5, 2019 Page 9 of 21
---	---	---

The number of subjects in the analysis and reasons for withdrawal will be summarized in a CONSORT flowchart. All subjects consenting to participate in the long term follow-up study will be reported as observed. No imputations are planned for missing data.

All statistical processing will be performed by Technomics Research LLC. The standard operating procedures (SOPs) of Tehcnomics Research LLC will be followed in the creation and quality control of all data displays and analyses. Analyses will be conducted using SAS® software Version 9.3 or later unless otherwise stated.

Statistical tests will be two-sided and will be performed at the 0.05 level of significance.

Descriptive statistics will be used for secondary endpoints and will include the number and percentage of subjects in each category. For continuous parameters, descriptive statistics will include n (number of subjects), mean, SD, median, minimum, and maximum. Appropriate inferential statistics will be used for the primary and secondary efficacy variables.

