#### **4.4.2 Primary Efficacy Analysis**

The efficacy analysis will be conducted all consented treated subjects with a 5+ year study visit. Results will be reported for observed data only; missing values will not be imputed.

The primary analysis will test the mean improvement in ODI from baseline to 5+ years as an intra-patient comparison. The mean change will be analyzed with an ANCOVA with a covariate of baseline ODI score. See Appendix A - Table 8.

If  $p \leq 0.05$  then it may be concluded that a significant functional improvement was demonstrated in axial low back pain subjects treated with the Intracept procedure and that the treatment is durable to mean follow-up for the long term study.

A comparison will be made between the ITT (as treated cohort) and a Intracept only treated cohort (with those subjects that had additional procedures such as RF Ablation, microdiscectomy, fusion, etc. removed).

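### The SAP's main analysis set is labelled ITT (as treated) but holds only consented subjects who attended a 5+ year visit, and no response rate is given over the full treated US arm

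*SAP*

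**What the plan says.** The label appears in two places. SAP 4.4.2 says "A comparison will be made between the ITT (as treated cohort) and a Intracept only treated cohort", the second cohort being the one from which subjects with additional procedures are removed. The sentence above Table 8 in Appendix A says "Tables 8 and 9 will be performed for both the ITT (as treated) population and the Intracept treated only population". The SAP's abbreviation list expands ITT as intent-to-treat, so the usual meaning of the term is invoked.

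The content of the set is also stated. SAP 4.4.2 opens with "The efficacy analysis will be conducted all consented treated subjects with a 5+ year study visit" and continues "Results will be reported for observed data only; missing values will not be imputed". SAP 4.1 adds "All subjects consenting to participate in the long term follow-up study will be reported as observed", and the protocol's section 6.1 likewise rules out imputation.

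The group from which these subjects come is larger. SAP 2.3 says "All US subjects that were randomized to the treatment arm of the original SMART Trial will be approached to participate", and SAP 2.1 describes the study as "follow-up in the 133 treatment arm subjects in the SMART trial in the U.S". Table 1 gives N=132 for the US treatment-arm cohort.

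**The concern.** Intention-to-treat conventionally means everyone randomised to the arm, and as-treated means everyone who received the procedure. These are different principles, and the SAP joins them into one name for a set that meets neither definition, because membership also requires consent and a completed telephone visit five or more years after treatment.

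The study has one arm and one visit, and SAP 4.4.2 allows a significant mean change to be read as evidence that the treatment is durable. Selective attendance is therefore a main threat to the conclusion. A reader who sees ITT beside the responder rates in Tables 8 and 9 may take them as rates in the whole arm, when subjects who died, declined or could not be found are not in the denominator. Nothing elsewhere in the plan supplies the full-arm figure.

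**Working it through.** **Step 1. Who is in the set.** The requirements for each definition, side by side:

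| Set | Randomised to treatment | Treated | Consented to follow-up | 5+ year visit done |
|---|---|---|---|---|
| ITT, usual meaning | yes | – | – | – |
| As treated, usual meaning | – | yes | – | – |
| SAP 4.4.2 efficacy set | yes | yes | yes | yes |

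The last two columns are what separate the SAP's set from both conventional ones.

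**Step 2. Could ITT here mean the full arm of 132 or 133?** No. A 5+ year visit is required, nothing is imputed, and the shells of Tables 8 and 9 are headed as follow-up subjects with N left open. The only contrast drawn is with the cohort that drops subjects who had additional procedures. The label therefore distinguishes keeping re-treated subjects from removing them, and does nothing else.

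**Step 3. Which tables are affected.** The labelling sentence covers Tables 8 and 9 (ODI and VAS change and responder rates). Composite success is in SAP 4.4.3.4 and Table 15, and neither uses the term. None of the three tables has a row with the full treated arm as denominator.

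**Step 4. How far attendance could move a full-arm rate.** The documents give no participation rate or responder-rate target, so there is no plan figure to reproduce. Inputs for the illustration:

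- p = 0.764, the 24-month rate of ODI response (10 points or more) in the SAP introduction, assumed to hold among attendees;
- N = 133, from SAP 2.1;
- n = 80, 100 or 120 attending (assumed; 60%, 75% and 90% of 133).

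Lower bound (all absent are non-responders) = p × n / N. Upper bound (all absent are responders) = (p × n + N − n) / N.

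| n | Lower bound | Upper bound |
|---|---|---|
| 80 | 61.12/133 = 46% | (61.12 + 53)/133 = 86% |
| 100 | 76.4/133 = 57% | (76.4 + 33)/133 = 82% |
| 120 | 91.68/133 = 69% | (91.68 + 13)/133 = 79% |

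The attendee-only rate is 76.4% in every row. The shortfall to the lower bound is about 30, 19 and 7 percentage points. With everyone attending it is zero.

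**Step 5. Sensitivity to the denominator.** With N = 132 and 100 attending, the bounds are 76.4/132 = 57.9% and (76.4 + 32)/132 = 82.1%, against 57.4% and 82.3% with N = 133. One subject hardly moves the result, but a full-arm row cannot be printed until the count is settled.

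**The case against.** The strongest reply is that the SAP is open about its method. Section 4.4.2 says who is analysed and that data are observed only. Section 4.1 plans a CONSORT flowchart. Table 1 reports refusals, withdrawals, losses and deaths against the treatment-arm cohort. Tables 2 to 7 and 11 compare subjects in and out of follow-up, including 3-month ODI and VAS change. The table shells themselves are headed as follow-up subjects, not as ITT. Keeping re-treated subjects in is a real, if partial, ITT feature, and nothing in the SAP claims that the label guards against loss to follow-up.

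Most of this stands, and it rules out three stronger readings. A reader might infer that losses are concealed; the attrition tables show otherwise. A reader might infer that composite success would be reported as ITT; Table 15 carries no such label. A reader might take the 46% to 86% range as the size of the labelling error; it is the effect of non-attendance, and renaming the set changes no number.

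The reply does not rescue the label, which still states a property that the set lacks. Nor do the planned comparisons stand in for a full-arm figure: those tabulated use baseline data, treated levels and 3-month outcomes, and cannot show what absent subjects' 5-year results would have been.

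A further objection is that counting absentees as non-responders is imputation, which both documents exclude. That is a fair reason to show the result only as a pair of bounds, outside the main analysis.

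**Conclusion.** The label ITT (as treated) is wrong in both places where it names the main set, and the plan reports no responder or success rate over the full treated US arm. The labelling finding rests on the text alone and needs no assumption.

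The numerical illustration depends on an assumed attendance and on a borrowed 24-month rate. Under those, the full-arm rate could lie anywhere from 46% to 86% with 80 of 133 attending, narrowing to 69% to 79% with 120. These are limits, not estimates of bias: the documents give no ground for expecting either extreme.

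The point does not invalidate the primary analysis. The test of mean ODI change is planned and described as an observed-case analysis, and bounds on responder rates say nothing direct about that mean. What the bounds show is how far the responder and success rates offered in support of durability depend on who attended.

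**What to change.** 1. In SAP 4.4.2 and in the sentence above Table 8, replace the ITT (as treated) wording with *5+ year observed cohort (including subjects with additional procedures)*.
2. In the observed-cohort versions of Tables 8 and 9, and in Table 15, add sensitivity rows giving each responder and success rate over all treated US subjects, with non-attendees counted first as all non-responders and then as all responders. Label the rows as bounds and not estimates. They are not asked for in the Intracept-only versions, since later procedures among non-attendees may be unknown.
3. State in the SAP that these rows are a sensitivity display, and that the observed-case primary analysis and the no-imputation rule in the protocol and SAP are unchanged.
4. Reconcile the full-arm denominator: 133 in SAP 2.1 and the protocol, 132 in SAP Table 1.

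The cost is a wording change, a few table rows, and publication of a lower figure that is less favourable than the attendee rate. No new data are needed.

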The primary efficacy endpoint for the original study was the 3-month change in Oswestry Disability Index (ODI) compared between the study arms. This comparison, as previously reported, found that at 3 months the per-protocol (PP) treatment group exhibited a 20.5 Least Squares Mean (LSM) improvement in ODI compared to a 15.2 LSM improvement in the sham group ( $p = 0.019$ ). The PP treatment arm subjects exhibited a durable ODI mean improvement (23.4 points) at 24 months. In terms of percent improvement in ODI from baseline, these results translate into mean percentage improvements of 46.2% at 12 months and 53.7% at 24 months. Responder rates for ODI and low back pain visual analogue scale (VAS) were also maintained through two years, with patients showing clinically meaningful improvements in both: ODI  $\geq$  10-point improvement in 76.4 percent of patients and ODI  $\geq$  20-point improvement in 57.5 percent; VAS  $\geq$  1.5 cm improvement in 70.2 percent of patients. Patients receiving the Intracept Procedure also decreased utilization of opioids and spinal injections as compared to utilization prior to treatment.

The purpose of this study is to measure the long term (5 + years) effectiveness outcomes in subjects treated with the Intracept Procedure in this original SMART study population.

 relevant medsystems	CD_3012_Rev B  Five-Plus Year Follow-Up of SMART Trial Statistical Analysis Plan	Date Effective: November 5, 2019  Page 6 of 21
--	---	---

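### The SAP's regression-to-the-mean table tests each arm against zero and specifies no between-arm difference, so its tests cannot tell regression from a treatment effect

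*SAP*

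**What the plan says.** SAP section 4.4.3.3 gives one sentence of method: "Regression to the mean analyses for ODI and VAS will be performed as supplemental analyses". It then refers to Table 11, but the table with that title in Appendix A is Table 10. Table 11 compares participants with non-participants.

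Table 10 reports, for ODI, "Average change in ODI in CONTROL group between baseline and 1 year" and "Average change in ODI in CONTROL group between baseline and 2 years", then the Intracept counterparts, starting with "Average change in ODI in INTRACEPT group between baseline and 1 year". It continues with "Average change in ODI in INTRACEPT group between baseline and 5+ years", which has no control counterpart, and "Time (per year) effect on ODI in INTRACEPT group". The VAS rows follow the same pattern; the last control row is "Average change in VAS in CONTROL group between baseline and 2 years". Every row asks for a mean, N, 95% CI and a p-value. The null hypothesis is zero change in the change rows and zero slope in the two time rows. The single column is headed as the SMART 5+ year follow-up subjects.

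The primary analysis (SAP 4.4.2) is a within-patient comparison of ODI at baseline and 5+ years. A significant result permits the conclusion that functional improvement was demonstrated and is durable. Only US treatment-arm subjects are approached (SAP 2.3).

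**The concern.** A change from baseline in one arm mixes the effect of treatment with whatever would have happened anyway. Regression to the mean is a leading rival explanation for such a change, and Table 10 is where the SAP takes it up. The control arm of a randomised trial is the natural tool, because regression to the mean acts on both arms alike and cancels in their difference.

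Table 10 brings in the control arm but does not take the difference. Each arm is tested against zero, which is the hypothesis that regression to the mean would itself falsify. A completed table could show small p-values throughout and be read as answering the rival explanation when the tests have not addressed it. What is at stake is how the durability conclusion is interpreted. Whether the primary test succeeds is a separate matter.

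**Working it through.** **1. What the rows test** (counted from Table 10)

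| Rows | Arm | Visits | Null hypothesis |
|---|---|---|---|
| 4 | Control (ODI, VAS) | 1 and 2 years | change = 0 |
| 6 | Intracept (ODI, VAS) | 1, 2 and 5+ years | change = 0 |
| 2 | Intracept (ODI, VAS) | time slope | slope = 0 |
| 0 | Intracept minus control | none | none |

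No other SAP section specifies a between-arm contrast or an arm-by-time term.

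**2. The only sham figures in the documents.** SAP section 1 says that at 3 months the per-protocol treated group "exhibited a 20.5 Least Squares Mean (LSM) improvement in ODI compared to a 15.2 LSM improvement in the sham group", with p = 0.019.

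- Difference: 20.5 − 15.2 = 5.3 points. Ratio: 15.2 / 20.5 = 0.74.
- The p-value cannot be reproduced, because no SD and no per-protocol n per arm are given. It can be inverted: two-sided p = 0.019 corresponds to z = 2.346, so SE = 5.3 / 2.346 = 2.26, and the 95% CI is 5.3 ± 1.96 × 2.26, about 0.9 to 9.7.

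**3. The same data tested against zero.** With 2:1 allocation and a common SD, the sham-arm SE is 2.26 / √1.5 = 1.845 and the treated-arm SE is 2.26 / √3 = 1.305.

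- Sham: z = 15.2 / 1.845 = 8.2.
- Treated: z = 20.5 / 1.305 = 15.7.

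A direct version uses t = 15.2 / (SD/√n), with SD 16 to 20 and 50 to 75 controls (both assumed). It gives 15.2 / (20/√50) = 5.4 up to 15.2 / (16/√75) = 8.2. Either way the sham arm alone is far from zero, while the between-arm z is 2.3.

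**4. What the tests do when treatment adds nothing.** Suppose both arms change by 15.2 points. The rejection probability is approximately Φ(15.2/(SD/√n) − 1.96). Assumed range: SD 12 to 25, treated n 67 to 133, controls half of that.

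- Treated arm, worst case (SD 25, n 67): 15.2 / (25/√67) = 5.0, probability 0.9987.
- Sham arm, worst case (SD 25, n 33.5): 15.2 / (25/√33.5) = 3.5, probability 0.94.

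A test that rejects almost surely when the treatment effect is nil cannot discriminate between the two explanations.

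**5. What the missing rows would show.** If the 1- or 2-year difference were also 5.3 points (an assumption), the 95% CI half-width is 1.96 × SD × √(1/n_t + 1/n_c).

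- SD 12, n 133 and 66.5: 3.5 points, power 84%.
- SD 25, n 67 and 33.5: 10.4 points, power 17%.

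**6. Populations.** The column heading names 5+ year follow-up subjects. Only treatment-arm subjects enter this study, so the heading cannot describe the four control rows. It also leaves open whether the 1- and 2-year Intracept rows use the full arm or only those who attended at 5+ years. A comparison of attendees with all controls would not be a randomised one.

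**The case against.** The strongest reply is that Table 10 already holds what is needed. Each row gives a mean, N and 95% CI as well as a p-value, so a reader can subtract the arms at 1 and 2 years and approximate an interval. The control-arm mean change is itself an estimate of what happens without treatment, and it already sits in the same table as the 5+ year Intracept change. This stands against any reading that the table carries no information on regression to the mean: the limitation belongs to the specified tests. The derived difference would still be unplanned and unadjusted for baseline, and taken from populations the table leaves unclear.

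It can also be said that 1- and 2-year contrasts cannot show how much of the 5+ year change is due to treatment, because no control was followed that long. That is correct and limits what any fix can deliver. It is a reason to state the limit beside the 5+ year rows.

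Finally, the analysis is supplemental, carries no decision rule and names regression to the mean only. The control change would contain sham response as well, but the SAP does not claim to address that. This also stands, and it bears on priority.

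**Conclusion.** The point holds for the specified tests. None of the 12 rows compares the arms, and tests against zero would reject with near certainty whether or not treatment added anything: at least 99.8% in the treated arm under a nil effect. That figure assumes SD 12 to 25, n 67 to 133 and a common change of 15.2 points. The documents give no SD and no control results at 1 or 2 years.

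Some stronger inferences are not supported:

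- **That 74% of the long-term improvement is regression or sham response.** The ratio comes from 3-month per-protocol figures. It illustrates why zero is the wrong reference and says nothing about later visits.
- **That the arms are in fact drawn from incomparable populations.** The heading leaves this open; it does not show it.
- **That control subjects later received the active procedure.** Neither document mentions it.
- **That the primary result is invalid.** The primary test does not depend on Table 10.

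The change should be made, as an improvement to a supplemental analysis.

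**What to change.** - Add four rows to Table 10: the baseline-adjusted Intracept-minus-control difference in ODI and in VAS change, at 1 year and at 2 years, each with a 95% CI. Base them on all randomised US subjects with data at that visit.
- State the population for every row, including whether the 1- and 2-year Intracept rows are limited to 5+ year attendees.
- Say in section 4.4.3.3 that the within-arm p-values against zero will not be used as evidence against regression to the mean.
- State that no controlled contrast exists at 5+ years, so the control change at 1 and 2 years is only an external benchmark for the 5+ year Intracept change.
- Correct the cross-reference in section 4.4.3.3 from Table 11 to Table 10.

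The cost is a few table rows from parent-trial data of the kind the table already draws on, with no new data collection. The contrast may be imprecise, with a half-width of 3.5 to 10.4 ODI points over the assumed range, and it may look less favourable than the within-arm changes.
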